User-driven Retrospectively Supervised Classification Updating (RESCU) System for Robust Upper Limb Prosthesis Control

NCT04043234

December 29, 2023

This study will compare the use of RESCU [Experimental] Prosthesis with a [Standard] pattern recognition prosthesis in a clinical setting and in unsupervised daily activity. The protocol will follow a single case experimental design (SCED) to compensate for the limited size of the patient population. Each of the participants will use the Standard and Experimental systems over a 35-day period. The Standard system will include a multi-articulated hand, eight EMG electrodes, and a commercially-available pattern recognition controller. The *RESCU* system will also use the multi-articulated hand, similar to the Standard system, but will differ with respect to incorporating eight *IBT Element Electrodes* (as required for pattern recognition control) and the *RESCU* control software.

**Participants:** We will recruit a total of 10 unilateral trans-radial amputees based on the inclusion and exclusion criteria noted in the Clinical Protocol. Note: the *RESCU* system is applicable to a range of amputation levels, but this study is focused on trans-radial amputees as they represent the largest population of users.

**Procedures:** After informed consent and medical clearance are completed, participants will be fitted by the study prosthetist.

On **Day 0**, the participant will be evaluated with the Standard prosthesis. A series of **Measures** (as defined in the next paragraph) will then be recorded. The participant will then take the prosthesis home for 1 week, and daily use data will be recorded. The participant will return to the clinic for **Day 7 Measures** and download of the daily use data. During this same session, the participant will be fit with the second system, instructed on the controller's use, and **Measures** will be recorded. There will be no washout period as the prosthesis is expected to be in daily use. The participants will go home for a four-week period and return on **Day 35** for a second set of **Measures**. At this time, the participant will be asked which prosthesis he/she prefers, and this will be the prosthesis that they return home with at the end of the study.

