There are limited functional outcome assessment options for the planned comparison. However, we will test functional measures at the clinic appointments, examine daily use data, and administer several qualitative surveys to assess participant outcomes.

**Measures (each appointment day):** **First**, a validated measure of upper extremity impairment will be used: the Activities Measure for Upper Limb Amputees (AM-ULA). The AM-ULA is a clinician-graded measure of activity performance for adults with upper limb amputation that considers task completion, speed, movement quality, skillfulness of prosthetic use, and independence to quantify how functional an individual is while using their prosthesis. A higher score indicates overall greater prosthesis functionality. This test has been validated for normative data.

**Second**, we will ask participants to record daily use data with the Standard and Experimental systems:

**Mean Daily Prosthesis Use Duration:** Our hypothesis is that *RESCU* will improve prosthesis acceptance. In addition to the subjective measures used below, we will measure the mean duration of daily prosthesis use as a proxy for improved prosthesis acceptance. We will compare the mean daily use for the Standard and Experimental systems, hypothesizing that the Experimental system will be used more than the Standard system. **This will be our primary outcome measure.**

**Third**, we will use a suite of validated survey instruments directly related to prosthesis use and satisfaction. These instruments are the Orthotics and Prosthetics User Survey Upper Extremity Functional Status (OPUS-UEFS) [53], the Trinity Amputation Prosthesis Experience Scale (TAPES), and various Patient Reported Outcomes Measurement Information System (PROMIS) subscales (e.g., Pain Interference, Satisfaction Short Form 8a). In addition, we will report the percentage of participants that preferred the *RESCU* system.

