**Statistics:** Our primary outcome measure will be the mean daily prosthesis use duration. We hypothesize that the mean daily use for those using the Standard system will be increased from 4.0 to 6.0 hours. In order to detect such a difference, using a paired t-test calculating the mean difference between the use of the two systems, and assuming no period effect and no carryover effect, 10 pairs of measurements would be needed. A two-sided t-test achieves 80% power to infer that the mean difference is not 0.00 when the total sample size of a 2x2 crossover design is 20 (10 patients), the actual mean difference is 2.00, the standard deviation of the paired differences is 3.00, and the significance level is 0.050.

**Data analysis:** Data will be gathered and evaluated carefully by study team members without conflicts of interest to determine the distribution of all scores in the population studied and the variability of scores within and between uses of the two systems. We will specifically examine whether daily use improves by week of use. Personal

characteristics will be used to stratify analyses as applicable. As stated above, we will compare the mean daily use duration of the two systems using a paired t-test, and attempt to determine if there is a period effect, i.e., trend over time. We will also test to assure that there is no sequence effect. We anticipate that the system preferred by the participant will also demonstrate an increased mean daily use duration.

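### Every participant uses Standard first and RESCU second, so the promised sequence test cannot be run and the primary paired t-test cannot tell device from period

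*Combined protocol and SAP*

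**What the plan says.** All places are in the combined protocol and SAP.

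- **Opening paragraph:** "Each of the participants will use the Standard and Experimental systems over a 35-day period". It calls the study a single case experimental design.
- **Procedures:** on Day 0 "the participant will be evaluated with the Standard prosthesis". Then: "The participant will then take the prosthesis home for 1 week, and daily use data will be recorded". At the Day 7 visit: "During this same session, the participant will be fit with the second system". Then: "The participants will go home for a four-week period", ending on Day 35. On the changeover: "There will be no washout period as the prosthesis is expected to be in daily use".
- **Mean Daily Prosthesis Use Duration (primary outcome):** "We will compare the mean daily use for the Standard and Experimental systems".
- **Statistics:** a paired t-test, described as a 2x2 crossover with 10 patients, with period and carryover effects both assumed absent. Inputs are a mean difference of 2.00 h, a paired SD of 3.00 h and a two-sided 0.05 level.
- **Data analysis:** use by week will be examined and a period effect, defined as a trend over time, will be looked for. It then adds: "We will also test to assure that there is no sequence effect".

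There are only two systems and Standard comes first, so the second system is RESCU. No randomisation, counterbalancing or reverse order is described.

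**The concern.** A 2x2 crossover needs two groups that receive the systems in opposite orders. That is what lets the analysis separate device from period, and it is the only thing a sequence test can compare. The schedule described has one group.

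Two consequences follow. A pre-specified check, meant to give assurance about order, cannot be carried out. And the primary result would be read as an effect of RESCU on acceptance when it is a before-after difference that also contains any change in use over the 35 days: practice, familiarity, season, or the effect of being monitored. Such a change could create an apparent RESCU benefit or hide a real one.

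**Working it through.** **1. Can the effects be separated?** Take one row per participant and period, with columns for intercept, system, period and sequence.

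| Orders | System and period columns | Sequence column | Rank |
|---|---|---|---|
| One (as described) | identical | constant | 2 of 4 |
| Two (for example 5 and 5) | distinct | varies | 4 of 4 |

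With one order the sequence test has nothing to compare, and the paired difference estimates device effect plus period effect plus any carryover.

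**2. How a trend enters the primary difference.** This assumes that mean daily use averages all days on each system (days 1–7 and days 8–35).

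- Phase midpoints: (1 + 7)/2 = 4.0 and (8 + 35)/2 = 21.5.
- Gap: 21.5 − 4.0 = 17.5 days = 2.5 weeks.
- Shift in the primary difference = 2.5 × weekly trend.

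**3. Effect on the test.** Inputs from the Statistics paragraph: n = 10, paired SD 3.00, two-sided 0.05. The test has 9 df, critical value 2.262 and noncentrality = mean difference / (3.00/√10). The trends are assumptions, because the documents give none.

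*The plan's own figure first:* a mean difference of 2.00 h gives noncentrality 2.108 and power 46.9%, against the stated 80%. That gap is a separate issue; 46.9% serves here only as the baseline.

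| True device effect | Trend (h/week) | Shift (h) | Mean difference tested (h) | Noncentrality | Chance of significance |
|---|---|---|---|---|---|
| 0 | 0.2 | 0.5 | 0.5 | 0.527 | 7.6% |
| 0 | 0.4 | 1.0 | 1.0 | 1.054 | 15.7% |
| 0 | 0.8 | 2.0 | 2.0 | 2.108 | 46.9% |
| 2 h | 0 | 0 | 2.0 | 2.108 | 46.9% |
| 2 h | −0.2 | −0.5 | 1.5 | 1.581 | 29.3% |
| 2 h | −0.4 | −1.0 | 1.0 | 1.054 | 15.7% |

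**4. Can the planned trend analysis repair this?** Only in part. With daily data, a model with intercept, system and day has rank 3 of 3, so a trend-adjusted device step can be estimated. Adding days on the current system as a second time scale gives rank 3 of 4: calendar trend and practice on the current device cannot both be fitted alongside the step.

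The answer therefore depends on which trend is assumed. Take no device effect and 0.4 h per week:

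- *Calendar trend:* raw difference 0.4 × 2.5 = 1.00 h; adjusted step 1.00 − 1.00 = 0.00 h.
- *Practice that restarts with each device:* the mean day on device is 4.0 for Standard and 14.5 for RESCU, a gap of 10.5 days = 1.5 weeks. Raw difference 0.4 × 1.5 = 0.60 h; adjusted step 0.60 − 0.4 × 2.5 = −0.40 h.

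**5. Precision of the adjusted step.** With independent daily errors, in units of the daily error variance:

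- Unadjusted: 1/7 + 1/28 = 0.1786.
- Adjusted: 0.1786 + 17.5²/(28 + 1827) = 0.1786 + 0.1651 = 0.3437, where 28 and 1827 are the within-phase sums of squares of day.
- Ratio 0.3437/0.1786 = 1.92, so this part of the SE rises by √1.92 = 1.39. With day-to-day correlation 0.6 the ratio is 1.75 and the factor 1.32.

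If daily error makes up a share f of the paired variance of 9, the effective SD is 3 × √(1 − f + 1.92f):

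| f | SD (h) | Power for 2 h |
|---|---|---|
| 0 | 3.00 | 46.9% |
| 0.5 | 3.63 | 34.4% |
| 1 | 4.16 | 27.5% |

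**The case against.** **The plan discloses its assumption and already looks for trend.** True. The no-period, no-carryover assumption is stated, and analyses by week and over time are planned. But the assumption appears as a sizing input, one order cannot verify it, and step 4 shows that a trend analysis recovers a device effect only under a further untestable assumption.

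**The study is labelled a single case experimental design.** A fixed Standard-then-RESCU order is compatible with that label. The label supplies no second order, and the named primary analysis is a group paired t-test.

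**The averaging window is not stated.** This stands as a qualification. Using all days is the plain reading of mean daily use, but the text does not say which RESCU days count. At 0.4 h per week, using only the first RESCU week (days 8–14) gives a 0.4 h shift and 6.7% rejection; using only the last (days 29–35) gives 1.6 h and 32.6%. The multiplier changes; the confounding does not.

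**The trends are hypothetical.** They are, and 0.8 h per week is large: over five weeks it adds 4 h to a planned Standard mean of 4.0 h. The figures show sensitivity to a trend, not that one exists.

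**A second order may be described elsewhere.** The Participants paragraph cites a Clinical Protocol that is not available here, but only for eligibility.

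**The paired t-test can be run without the sequence test.** It can, but what it estimates still has to be stated correctly.

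**Conclusion.** The concern holds and must be fixed. As written, the sequence test is impossible, the crossover label contradicts the schedule, and the primary contrast is device and period combined. These conclusions follow from the fixed order and need no numerical assumption.

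The size of any bias is unknown, because the documents give neither the sign nor the magnitude of a trend. Averaging over all days on each system, and with n = 10 and SD 3.00, upward trends of 0.2 to 0.8 h per week would raise a nominal 5% error rate to between 7.6% and 46.9%. Downward trends of 0.2 to 0.4 h per week would cut the chance of detecting a true 2 h effect from 46.9% to between 29.3% and 15.7%.

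**What to change.** Reconcile Procedures with Statistics and Data analysis. If the order is fixed as described:

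1. Delete the 2x2 crossover label and the sequence test.
2. Insert: *All participants use Standard, then RESCU. The primary paired t-test estimates a before-after difference in mean daily use that includes any time or practice effect.*
3. State which days enter each mean.
4. Name one sensitivity analysis: a model of daily use with a device step and a common linear trend. State its assumptions: the trend is linear, the same in both phases, and tied to calendar time rather than restarting with the new device.

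**Cost:** wording and one extra analysis of daily data already collected, with no added patients or visits. The claim becomes weaker. The sensitivity model is also less precise: power for 2 h lies between 46.9% and 27.5%, depending on how much of the SD is daily error. It can support the primary test but not replace it.

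If a crossover was in fact intended, both orders must be described and a period-adjusted estimate used. That is a redesign, and the documents do not allow its cost to be worked out.
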